Gamma-aminobutyric acid (GABA) is the central inhibiting neurotransmitter in the human nervous system. Two GABA receptors are known to date: GABA_A and GABA_B. The stimulation of both receptors leads to a wide variety of effects on cognition, mood, vigilance, sleep and other neuropsychological functions. GABA_A and GABA_B receptor dysfunction seems to play a key role in stress, anxiety and depression (Cryan & Slattery, 2010). γ -Hydroxybutyrate (GHB) – a GABA metabolite - is an endogenous compound found in the human brain (Bessman and Fishbein, 1963). Central GHB releasing neurons and specific GHB receptors form the GHBergic neurotransmitter system, which function is still widely unknown (Maitre, 1997). Despite its high affinity to GHB receptors, most of its neuronal and behavioral effects are mediated by an agonist action at GABA_B receptors (Engberg and Nissbrandt, 1993). It was reported that GHB increases dopamine and norepinephrine levels in a biphasic mode (Maitre, 1997). GHB is approved for the treatment of narcolepsy in the USA and Europe and for alcohol withdrawal syndrome in Italy and Austria. However, GHB is also misused by a small part of the population: the most frequently reported reasons are recreation purposes, to enhance sex, to be sociable and to achieve altered states of consciousness (Sumnall et al., 2008). These effects seem to be associated with neuroendocrine alterations, which are mostly unknown in detail. An increase of growth hormone release is the most consistent finding (Van Cauter et al., 1997). In addition, plasma levels of cortisol and ACTH after GHB challenge indicated an activation of the HPA axis in the resting state, compared to an HPA axis inhibition under stress conditions (Nava et al., 2007). Neurosteroids and oxytocin are candidates of primary interest for the endocrine mediation of prosocial and prosexual behavior as suggested by animal studies (Baskerville et al., 2009, Frye et al., 2000). Thus, a release of these hormones might be an explanation for the contact stimulating effects of the drug. Interestingly, GHB is also an enhancer of slow wave sleep (SWS) in humans, which is a remarkable pharmacological property, given that most of the psychopharmacological drugs rather decrease SWS (Van Cauter et al., 1997). Recent studies have demonstrated that SWS is involved in declarative memory consolidation but the role of a combined stimulation of GABA_B and GHB receptors in SWS-mediated memory consolidation is widely unknown so far (Born and Wagner, 2009). Early studies also reported anxiolytic and antidepressant effects of GHB in psychiatric patients (Danon-Boileau et al., 1962, Rinaldi et al., 1967). Neuroimaging, especially functional magnetic resonance imaging (fMRI) and MR spectroscopy (MRS) have revolutionized psychiatric biomarker research. As such, assessing brain network connectivity patterns during resting state in healthy subjects and major depressive disorder (MDD) patients and modulating them with pharmacologic or other interventions, has proven to be one of the most promising strategies in the field (Phillips et al., 2015, Hasler and Northoff, 2011). In terms of molecular imaging, MRS has been established as a valid method to study pathological and therapeutic neurotransmitter alterations in mood disorders (Caverzasi et al., 2012), and growing evidence indicates alterations of brain GABA and Glutamate (Glu) concentrations in MDD (Jun et al., 2014, Chang et al., 2003, Hasler et al., 2007). The combination of assessing brain network connectivity patterns using resting state fMRI/EEG and brain GABA and Glu concentrations using MRS seems a most promising approach in current neuroimaging biomarker research and are implemented in the study presented here.

Moreover, the effects of GHB on putative plasma biomarkers for depression and sleep physiology, such as IL-6, IL-10, TNF- α , CRP, IL-4, IL-18 and IFN- γ , tryptophan, kynurenin, kynurenic acid, neopterin, malondialdehyd, qinolinsäure, IDO (indolamine-2,3-deoxygenase) and substance P are investigated in our study. The unique spectrum of effects of a combined GABA_B-/GHB receptor stimulation by GHB on neuropsychiatric functions such as sexual and prosocial behavior, neuroendocrine systems and sleep makes it a pharmacological research tool and model substance of high interest. Since there are no such systematic studies of a combined GABA_B-/GHB receptor stimulation in healthy human subjects, we aim to investigate the effects of GHB on sleep, pharmacokinetics, putative depression and sleep biomarkers, mood, cerebral GHB-, GABA- and Glu -concentrations, resting state fMRI, as well as cognitive and social functions in healthy volunteers. The study consists of two separate experiments (PUK-GHB01 and PUK-GHB02), including 32 participants in PUK-GHB01 and 20 participants in PUK-GHB02. Social cognition, brain activity and neuroendocrinology will be examined in the first, sleep architecture, pharmacokinetics, putative depression and sleep biomarkers, cognition, memory consolidation, as well as GHB-, GABA-, and Glu-MRS and resting state fMRI/EEG in the second experiment.

2. Background

2.1 Study substance

Sodium oxybate is the international drug name for the sodium salt of gamma-hydroxybutyric acid (GHB). In research the terms are used synonymously. GHB is merchandized as Xyrem® in the U.S., Canada and Europe (incl. Switzerland) by Jazz Pharmaceuticals, Valeant Pharmaceuticals International and UCB-Pharma. In these countries it is the first line treatment for excessive daytime sleepiness and cataplexy in patients with narcolepsy. GHB is approved in Germany as an anesthetic, Somsanit® (Dr. F. Köhler Chemie) and is approved in Austria and Italy for the treatment of opioid and alcohol withdrawal as Alcover® (Laboratorio Farmaceutico). In Switzerland, GHB is a controlled substance (category A+). In this study Xyrem® oral solution will serve as source for GHB, which is used as a model substance for a combined GABA_B-/GHB receptor stimulation.

2.2 Dosing

The dosing used in our two studies will be lower than the common therapeutic dosing of GHB. The usual starting dose for the treatment of narcolepsy is about 4.5 g/night (about 65 mg/kg), split into 2 equal doses: one immediately before going to bed, the second 2.5-4 hours later. The dose can be increased up to a maximum of 9 g/night (about 130 mg/kg). The proper dose has to be found individually under supervision of an experienced physician. Once established, the individual dose is taken nightly as long as the disorder persists (Compendium, 2010). In the treatment of alcohol withdrawal syndrome (AWS) and prevention of relapses, GHB is given during daytime. The usual application is a daily total of 3.5-7 g (about 50-100 mg/kg) in 3 divided doses (Boscolo-Berto et al., 2012).

2.2.1 PUK-GHB01: social cognition and hormones

In the first two sessions of the first trial, we will give either 20 mg/kg (corresponding to 1.4 g in a 70 kg subject, n=16) and 35 mg/kg (corresponding to 2.45 g in a 70 kg subject, n=16) compared to placebo, to test dose-dependent effects of GHB on social cognition and neuroendocrine parameters. In the third and fourth session of the first trial, we will give 35 mg/kg (n=32) compared to placebo. These doses are low and medium, respectively, compared to the therapeutic doses used in narcolepsy. In other studies concerning subjective or cognitive effects of GHB, doses such as 10 mg/kg (Grove-White and Kelman, 1971), 21 mg/kg (Delay et al., 1965), 15 mg/kg vs. 30 mg/kg (Rosen et al., 1997), 16-64 mg/kg (Carter et al., 2009a) up to 40-72 mg/kg (Abanades et al., 2006) were used. The dose selected for our first trial is promising in mediating

significant subjective and cognitive alterations, without causing too many unwanted side effects such as dizziness, nausea and somnolence.

2.2.2 PUK-GHB02: sleep and memory

In the second trial, we will give 50 mg/kg GHB compared to placebo, to test the effects of the drug on sleep architecture, the electroencephalogram (EEG) in sleep and wakefulness, neuroendocrine parameters, pharmacokinetics, depression and sleep biomarkers, cognition, and memory consolidation during sessions 1 and 2. We will give the same dose vs. placebo to assess the concentrations of GHB, GABA and Glu in sleep- and depression-related brain areas using MRS/EEG and resting state connectivity using fMRI/EEG during sessions 3 and 4 (see figure 1). This dosage is used commonly in the treatment of narcolepsy. In comparable studies concerning GHB-mediated effects on sleep, doses such as 1 x 35-50 mg/kg (Van Cauter et al., 1997), 1 and 2 x 64 mg/kg (Rosen et al., 1997), 2 x 42 mg/kg (Scharf et al., 2003) and 2 x 42-64 mg/kg (Ondo et al., 2008) were used. The dose selected for our second trial is common both in therapeutic trials and scientific studies and is promising in mediating significant effects on sleep architecture, the EEG, pharmacokinetics, depression and sleep biomarkers, cognition, neuroendocrine parameters and memory consolidation. Before inclusion in the study, all subjects will be screened regarding the presence of specific sleep disorders (e.g. sleep-related breathing disorders) by using polysomnography.

[figure not shown]

Figure 1: Basic Flow Chart of PUK-GHB02

2.3 Side effects

Typical side effects (10-20% of the treated patients) of GHB are dizziness, nausea and headaches. Common side effects ($\geq 1/100$ to $< 1/10$) are anorexia, abnormal dreaming, drowsiness, disorientation, somnambulism, depression, sleep disturbances, cataplexy, fear, insomnia, nervousness, somnolence, tremor, imbalance, falls, attention deficits, hypesthesia, paresthesia, sedation, blurred vision, arterial hypertonia, dyspnea, snoring, emesis, gastric pain, diarrhea, sweating, muscle cramps, arthralgia, enuresis, asthenia, sleepiness, peripheral edema. Occasional side effects ($\geq 1/1000$ to $< 1/100$) are weight loss, psychosis, paranoia, abnormal thinking, hallucinations, agitation, suicide attempt, sleep disorder, myoklonus, amnesia, restless leg syndrome, eczema (Compendium, 2010).

2.4 Toxicity

The toxic effects of GHB are dose-dependent: low doses (10 mg/kg) induce euphoria, increased libido, and disinhibition, while doses of 30-50 mg/kg lead to sleep and general anesthesia (Wong et al., 2004). The median lethal dose (LD_{50}) of GHB in rats is 1.7 g/kg (Snead, 2002). In humans, massive overdoses and the combination of GHB with CNS depressants such as alcohol are associated with serious coma necessitating

intubation and intensive care, the number of reported fatal cases associated with the drug appears very limited. Post-marketing surveillance indicates GHB has an acceptable safety profile for controlled clinical application (Wedin et al., 2006).

3 Aims of the project

3.1.1 PUK-GHB01: social cognition and hormones

The GABAergic system is the principal mediator of neuronal inhibition in the brain. Dysfunction of GABA neurotransmission has been proposed to play a key role in psychiatric disorders, including anxiety and depression. While the link between GABA and anxiety is clearly established, the importance of GABAergic dysfunction in the etiology and course of depression remains unclear. Animal studies showed that alterations of GABA_B receptor function cause antidepressant-like behavior (Cryan and Slattery, 2010). Some human studies indicate a beneficial effect of the GABA_B agonist baclofen on depression symptoms (Krupitsky et al., 1993). Baclofen is further known to impair cognition by its sedative effect and to increase concentrations of both growth hormone (Cavagnini et al., 1977) and cortisol (Morosini et al., 1985). GHB is an endogenous short-fatty acid and GABA metabolite found in the human brain (Bessman and Fishbein, 1963). Despite its high affinity to GHB receptors, most of its neuronal and behavioral effects are mediated by an agonist action at GABA_B receptors (Engberg and Nissbrandt, 1993). Presumably, exogenous administered supraphysiological concentrations of GHB produce qualitatively different neuronal actions than those produced by endogenous GHB concentrations. In high concentrations GHB might act on the high affinity GHB receptor and on the GABA_B receptor, as the neuronal and behavioral effects of GHB and the specific GABA_B agonist baclofen can be differentiated experimentally (Wong et al., 2004). GHB was reported to increase dopamine and norepinephrine levels in a biphasic mode (Maitre, 1997). A certain concern regarding the use of GHB for research purposes is its abuse and addictive potential. The drug is abused by a small percentage of the population (<1%) as a recreational drug in a home setting or as a "club drug" (Sumnall et al., 2008). The development of addiction in patients treated with GHB is rare (0.015 %) compared to illicit use (4-21 %) (Carter et al., 2009b). The subjective effects of GHB constitute a continuum between relaxation, prosocial and prosexual stimulation in lower doses (10 mg/kg) up to profound sedation and sleep-induction in higher doses (50 mg/kg) (Bosch et al., 2012). GHB-mediated effects seem to be associated with neuroendocrine alterations, which are mostly unknown in detail. An increase of growth hormone release is the most consistent finding (Van Cauter et al., 1997). The effects of GHB on the hypothalamic-pituitary-adrenal (HPA) axis were examined in several trials, but the results remain controversial. Plasma levels of cortisol and ACTH after GHB challenge indicated an activation of the HPA axis in the resting state, compared to an HPA axis inhibition under stress conditions (Nava et al., 2007). Neurosteroids and oxytocin are candidates of primary interest for the endocrine mediation of prosocial and prosexual behavior as suggested by animal studies (Baskerville et al., 2009, Frye et al., 2000). In humans, the prosocial effects of methylenedioxymethamphetamine (MDMA, "ecstasy"), which phenomenologically resemble to GHB-effects, correlated with a rise in plasma oxytocin levels (Dumont et al., 2009). Therefore, we propose to investigate the effects of a combined GABA_B/GHB receptor stimulation on the relations of social cognition and neuroendocrine parameters compared to placebo in 32 healthy subjects. GHB will serve as a model substance for the combined GABA_B/GHB receptor stimulation. The first experiment will focus on the acute effects of GHB in waking participants, assessing correlating changes in cognitive capacities, brain activity and endocrine blood parameters. We hope to gain new insights into the neurobiological underpinnings of prosocial and prosexual experience and behavior by these means. As anhedonia, reduced social interaction and loss of libido are key symptoms of depression, we aim to investigate the potential relevance of a combined GABA_B/GHB receptor stimulation for these psychobiological targets.

3.1.2 PUK-GHB02: sleep and memory

The GABAergic system is strongly involved in the regulation, maintenance and termination of sleep. Benzodiazepines, which mainly exert their effects via GABA_A receptor activation, have sedating and sleep-inducing effects, but clearly interfere with physiological sleep architecture. Although the restorative function of sleep seems intuitively obvious, some researchers follow the hypothesis that a primary function of sleep pertains to the consolidation of memory (Born and Wagner, 2009). Encoding and retention of information are understood as complementary processes which need distinct neuronal activation patterns for their realization. Memory consolidation serves the strengthening of newly encoded, preliminary memory traces. Recent studies could demonstrate that sleep after learning enhances retention not only of declarative memory (Gais and Born, 2004), but also of emotional (Wagner et al., 2001), and procedural memories (Stickgold, 2005). Moreover, the type of memory consolidation is dependent on specific sleep stages. It was shown that retention of hippocampus-dependent declarative memory benefits mainly from SWS-dominated early nocturnal sleep, whereas amygdala-dependent emotional memories and also procedural memories improve from REM sleep during the late night in the first place (Gais and Born, 2004). Brain stimulation that enhanced SWS oscillations was found to enhance selectively the retention of declarative memories in humans (Marshall et al., 2006). A previous study has shown that GHB is a robust enhancer of slow wave sleep (SWS) in patients with sleep disorders and in healthy subjects (Van Cauter et al., 1997). A deteriorative effect of GHB on memory encoding was shown in humans (Carter et al., 2009a, Grove-White and Kelman, 1971). Given, that encoding and consolidation of information are functional counterparts and that GHB reliably induces SWS, an enhancement of declarative memory consolidation under the influence of GHB seems convincing. Impaired sleep is a key symptom of depression, and brain resting state network alterations offer plausible mechanisms for antidepressant treatment effects related to sleep (Bosch et al., 2013). Moreover, alterations of GABA and glutamate concentrations can be found in patients with MDD (Jun et al., 2014, Chang et al., 2003, Hasler et al., 2007), potentially serving as diagnostic and therapeutic biomarkers. GHB has distinct neurobiological and clinical effects, which make it an interesting tool for the pharmacological modification of depression biomarkers (Bosch et al., 2012). This attempt is absolutely novel, as it has never been performed in humans to date. Therefore, we want to apply MRS/EEG of the anterior cingulate cortex (ACC), Nucleus accumbens (Nacc), and amygdala and assess resting state connectivity using fMRI/EEG directly after GHB-induced sleep (50 mg/kg GHB p.o. vs. placebo) and on the following morning in sessions 3+4 of experiment PUK-GHB02 (see figure 1). Hence, we propose to investigate the effects of GHB on sleep architecture, pharmacokinetics, and putative depression- and sleep biomarkers, cognition, declarative memory, as well as GHB-, GABA-, and Glu-MRS/EEG and resting state fMRI/EEG compared to placebo in 20 healthy subjects. The proposed study will provide the unique opportunity to investigate the neurobiology of a combined GABA_B-/GHB receptor stimulation on the regulation of sleep and memory. Given that the interest in the neurobiology of memory and sleep and their possible correlation to plasma, saliva and cerebral changes, is constantly increasing, a better understanding of the possible neurochemical consequences of GHB application is an appealing research approach. Memory deficits and sleep disturbances are characteristic symptoms of major depressive disorder. In this study, GHB serves as a model compound for a combined GABA_B-/GHB receptor stimulation, which could help to develop new treatments targeting specific neurobiological alterations in affective disorders.

3.2 Open questions

3.2.1 PUK-GHB01: social cognition and hormones

Since the discovery of GHB in the year 1960, an extensive body of research has been performed concerning its neurobiological effects in animals and humans. Its potency to induce pleasurable feelings, affiliative behavior and sexual arousal led to illicit use of GHB for recreational purposes. In spite of these facts, neither the prosocial and prosexual effects of GHB, nor the underlying neuroendocrine alterations were examined scientifically so far. Various hormones were shown to be involved in the processing of social cognition,

appetitive behavior and binding. It is most likely that the neuropeptide oxytocin plays a central role for the subjective and behavioral effects of GHB, as the secretion of this hormone was shown to correlate with the prosocial effects of the phenomenologically comparable club drug MDMA (Dumont et al., 2009). Other hormones of interest are centrally synthesized progesterone analogs such as alloprenanolon (3 α , 5 α -THP) and allotetrahydrodeoxy-corticosterone (THDOC). These neurosteroids are released after GHB application in rats and induce prosexual behavior (Barbaccia, 2004). Additionally, the results regarding the GHB-modulation of the HPA axis remain contradictory and need further investigation. The relations of GHB-mediated subjective and behavioral changes to alterations of cerebral activity and neuroendocrine function remain unstudied.

3.2.2 PUK-GHB02: sleep and memory

As mentioned above, a complementary effect of memory encoding and consolidation and a link of these processes to the wake-sleep cycle has been postulated. Declarative memory consolidation was related to early night SWS. If GHB enhances declarative memory consolidation possibly due to an enhancement of SWS remains unknown. GABA and glutamate neurotransmission are key players both in MDD (Phillips et al., 2015, Hasler and Northoff, 2011), and sleep physiology (Ackermann and Rasch, 2014). GHB was proposed as an experimental therapeutic in depression and interesting tool for the pharmacological modulation of depression biomarkers (Bosch et al., 2012). Here, we want to add data about cerebral GABA, Glu, and GHB concentrations in the ACC, Nacc, and amygdala and resting state connectivity in depression-related networks, with regard to a potential use of GHB as biomarker modulator in depression. In summary, the complex relationships of the GHB and GABA_B receptor mediated GHB effects on sleep architecture, EEG, pharmacokinetics, depression- and sleep biomarkers, cognition, memory, as well as GHB-, GABA-, and Glu-MRS/EEG and resting state fMRI/EEG pose various questions, which are addressed in the proposed study.

3.3 Working hypotheses

We expect to find significant alterations of sexual arousal, social cognition, pharmacokinetics, depression and sleep biomarkers, cerebral GHB-, GABA-, and Glu-concentrations, resting state connectivity, cognition, and declarative memory functions after GHB administration compared to placebo. Moreover, we predict that these effects are correlated with specific changes in serum biomarker levels, brain activation patterns and sleep architecture, respectively.

4 Study design

4.1 Primary outcome measures

In the first part of the study (PUK-GHB01), plasma hormone levels, subjective effects assessed by questionnaires, and social cognition parameters assessed by specific computed test batteries, as well as brain activity assessed by electroencephalography (EEG) and functional magnet resonance imaging (fMRI) will serve as primary outcome measures. The results of the neuropsychological test battery performance will serve as longitudinal safety parameters to detect unexpected cognitive impairment after GHB intake. In the second part (PUK-GHB02), plasma hormone levels, GHB levels in plasma, urine, hair, and nails, sleep biomarkers such as brain-derived neurotrophic factor (BDNF), fragile x mental retardation protein (FMRP), IL-beta, IL-6, IL-10, TNF-alpha, CRP, IL-4, IL-18 und IFN-gamma, tryptophan, kynurenin, kynurenic acid, neopterin, malondialdehyd, qinolinsäure, IDO (indolamine-2,3-deoxygenase), substance P, and genetic markers, cognition, memory consolidation assessed by procedural and declarative memory tests, polysomnographic parameters, cerebral GHB-, GABA-, and Glu-concentrations in the ACC, Nacc, and amygdala, resting state connectivity, and measures of daytime sleepiness such as the Epworth Sleepiness

Scale (ESS), as well as subjective mood measures such as the Visual Analog Mood Scale (VAMS), and the Positive and Negative Affect Scale (PANAS) will serve as primary outcome measures.

4.2 Design of the Experiments PUK-GHB01 and PUK-GHB02

4.2.1 PUK-GHB01: social cognition and hormones

Thirty-two male healthy subjects will be assessed with questionnaires (GHB Specific Questionnaire [GSQ], Sexual Arousal and Desire Questionnaire [SADI], Profile of Mood States [POMS], Visual Analog Scale [VAS]), tests of social cognition (Sexual Arousal Task [SAT], Multifaceted Empathy Test [MET], Social Gaze Test [SGT], Movie for the Assessment of Social Cognition [MASC]), neuropsychology (Cambridge Neuropsychological Automated Test Battery [CANTAB], Flanker Task, Verbal Memory Test [VLMT]), neuroeconomic tests (Reciprocity Task [RT], Social Value Orientation [SVO], Charity Donation [CD]), electroencephalography (EEG), functional magnet resonance imaging (fMRI) and neuroendocrine blood tests (oxytocin, 3,5-THP, THDOC, ACTH, prolaktin, testosterone, cortisol, progesterone, N-Arachidonoylethanolamin, 2-Arachidonoylglycerol, Palmitoylethanolamid, Arachidonic acid, Linoleboylethanolamid, Oleoylethanolaid, Stearoylethanolamid, prostaglandin E2 and GHB) after application of GHB (days 1+2 20 or 35 mg/kg p.o., days 3+4 35 mg/kg p.o. vs. placebo – cross over design). The neuropsychological and neuroeconomic test as well as the tests of social cognition have already been implemented in trials of the Experimental and Clinical Pharmacopsychology research group of the Psychiatric University Hospital Zurich. The neurocognitive test will be performed on a study computer of the experimental and clinical pharmacopsychology research group of the Psychiatric University Hospital Zurich. The fMRI experiments will be performed at the MR Center of the University Hospital of Psychiatry Zurich. The assessment will follow the Good Clinical Practice (GCP) guidelines. Both neurocognitive and neuroendocrine tests will be performed paralleled, under two different conditions (20 or 35 mg/kg GHB p.o. vs. placebo; t₀= GHB application) on two days spaced at least 1 week apart. Neurocognitive testing will be performed during the peak of subjective GHB effects (t+ 30 until t + 90). Blood tests for neuroendocrinologic measures will be taken six times (t-30 min, t₀, t + 20 min, t + 35 min, t + 65 min, t +95 min, t + 124 min and t + 180 min). A total amount of blood of 150 ml will be taken during each experiment. The complete assessment will last about five hours. The two fMRI sessions will start at least one week after the two first experimental days, and succeed with at least one week in between. Each session takes a time of 2.5 hours. Furthermore, one pre- and one post-test session will be performed for medical check-up.

All experiments are monitored by a medical doctor. In case of any unexpected incidence threatening the subject's health or if the subject wishes to abandon the study, the procedure will be stopped immediately. All participants will provide urine for a drug screening to control for current drug use. Any drug use pattern will be assessed using the Interview for Psychotropic Drug Consumption (Quednow et al., 2004). The subjects will receive 225 CHF for participating in the first to experimental days and the pre- and post-tests. An additional amount of 75 CHF can be earned through the neuroeconomical tests. The participation in the two fMRI sessions will be compensated with additional 100 CHF.

[figure not shown]

Chart 1 Order of study sessions

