
III, T7: the day after experimental night IV), seven sweat samples (one sweat patch per night), four urine samples (after every adaptation and experimental night), nine nail samples (weekly nail clipping). A total amount of blood of 250 ml will be taken during the whole experiment GHBO2. The experiment is monitored and all blood drawings are conducted by a medical professional or study nurse. In case of any unexpected incidence threatening the subject's health or if the subject wishes to abandon the study, the procedure will be stopped immediately. All participants will provide urine for a drug screening and absolute exhalative alcohol testing to control for current alcohol and drug use. Any drug use pattern will be assessed using the Interview for Psychotropic Drug Consumption (Quednow et al., 2004). Screening of all subjects includes a daytime screening examination and screening-night in the sleep laboratory, to exclude the inability to sleep in an unknown environment and the presence of specific sleep disorders (e.g. sleep-related breathing disorders, leg movements during sleep). Subjects will receive 800 CHF for participating in the study, plus additional 100 CHF for the hair samples on T4, and another optional 50 CHF for the nail samples.

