4.7.2 Blinding procedure

Blinding will occur through a clinical staff member not involved otherwise in the study. This person will randomly abstract GHB (Xyrem) or placebo (0.9% saline solution) for each subject and put it into a plastic cup with 150 ml standard orange juice using a ml-syringe. In the first experiment (SocCog) sixteen subjects will receive 20 mg/kg and sixteen subjects 35 mg/kg GHB on one occasion and placebo on the other. For the MR-sessions, the same thirty-two subjects will receive 35 mg/kg GHB in one, placebo in the other session in a double-blind, randomized manner. In the second experiment 20 subjects will receive 50 mg/kg GHB on two occasions and placebo on two others. The information about the weight of the subject is transmitted anterior to this procedure. The cup is labeled with the study-code and will be kept back until the end of the study. When the cup is filled, it will be given to the principal investigator, who hands it out to the subject. The subject drinks the whole content and returns the empty cup to the principal investigator.

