5.3 Exclusion criteria

We will exclude female subjects, persons with intake of illegal psychotropic substances more than 5 times per substance or any psychiatric axis I disorder according to DSM-V or existence of a serious somatic or neurological disease. Screening will be performed using DIA-X. To exclude current illegal substance use drug urine test will be done at the beginning of each test session.

	Inclusion	Exclusion
General	
 - the subjects capability to give informed consent must be approved by a psychologist or resident physician involved in the study - an informed consent form must be signed by the subject before the start of the test 	
 - women - lifetime intake of illegal psychotropic substances on more than 5 occasions per substance - psychiatric axis I disorder according to DSM-IV - existence of a serious somatic or neurological disease -homosexual - smoking - medication
additional for PUK-GHB01	
 - men between 20 and 40 years - heterosexual 	
 - metal implants and big tattoos
additional for PUK-GHB02	
 - men between 20 and 30 years 	
 - sleep abnormalities (e.g. sleep apnea syndrome) (wakefulness after sleep onset > 20 %, apnea/hypopnea index > 5/hour of sleep, number of periodic leg movements > 5/hour of sleep) - metal implants and big tattoos

Table 3 Inclusion and exclusion criteria of subjects

6 Assessments of Effects

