7.2 Security management in case of unexpected adverse effects

Each series of experiments will be supervised by a clinical doctor. Special attention will be paid to the possible occurrence of side effects, such as disinhibition, dizziness, nausea, drowsiness and respiratory impairment. In case of unexpected adverse effects, immediate help and quick transfer to an emergency unit is guaranteed.

8 Statistics

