8.5 Drop outs

Drop outs will be excluded from the study.

9 Study specific precautions and obligations

9.1 Specific precautions.

For the study participants it is not allowed to use any illegal drugs during or seven days prior to the experiments. Participants should abstain from alcohol at least 48 h hours. Furthermore, it is not allowed to drive motor vehicles or to use machines subsequent to the experiments.

10 Investigators obligation

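### PUK-GHB01 specifies no alcohol test before any of its up to 64 GHB doses, although PUK-GHB02 tests for alcohol before dosing on every experimental night

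*Combined protocol and SAP*

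**What the plan says.** The two experiments have parallel sentences on pre-session checks.

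- PUK-GHB01 (Section 4.2.1): "All participants will provide urine for a drug screening to control for current drug use".
- PUK-GHB02 (Section 4.2.2): "All participants will provide urine for a drug screening and absolute exhalative alcohol testing to control for current alcohol and drug use".

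Section 5.3 adds a check for both experiments: "To exclude current illegal substance use drug urine test will be done at the beginning of each test session". Section 9.1 gives the rule on alcohol: "Participants should abstain from alcohol at least 48 h hours". It does not say before what; before each experiment is the natural reading.

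Section 2.4 describes the hazard. Massive overdoses and "the combination of GHB with CNS depressants such as alcohol are associated with serious coma necessitating" intubation and intensive care. The same section says of dose, "while doses of 30-50 mg/kg lead to sleep and general anesthesia".

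For the response to trouble, Section 4.2.1 has a medical doctor monitor all experiments, and Section 7.2 promises: "In case of unexpected adverse effects, immediate help and quick transfer to an emergency unit is guaranteed".

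**The concern.** The protocol names a serious hazard, tests for it in one experiment and specifies no test in the other, without giving a reason. Followed as written, a man who drank despite the instruction would receive GHB in PUK-GHB01 unless someone noticed.

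Participant safety is the main issue. Supervision and emergency transfer act mostly once effects have appeared, whereas a breath test can prevent the combined exposure. A secondary gain would be less noise in the GHB-placebo comparison, since alcohol affects many of the same outcomes. Session order is randomised, so no systematic bias is claimed.

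**Working it through.** The plan gives no figure of its own on this point. The check is a comparison of the texts, followed by a count of the doses and sessions affected.

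**1. Is an alcohol test specified anywhere for PUK-GHB01?**

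| Place | What it lists for PUK-GHB01 | Alcohol test? |
|---|---|---|
| 4.2.1, design text | urine drug screen | no |
| 5.3, session-start check | urine test for illegal substances | no |
| 6.1, Table 4 | questionnaires, tasks, blood for endocrinology, scans | no |
| 7.1, Table 5 | blood pressure and pulse, days 1+2 only | no |
| 9.1 | abstinence instruction | no |
| 12.4, CRF content | drug screening | no |

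**2. What does PUK-GHB02 do?** In the Section 6.2 flow chart the dose is at 23:30 on each experimental night. The combined drug and alcohol test is at 20:40 on nights 1 and 2 (23:30 − 20:40 = 2 h 50 min before the dose) and at 21:30 on nights 3 and 4 (2 h before). The adaptation nights, on which nothing is dosed, also have one.

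**3. Could the PUK-GHB01 drug screen be meant to include alcohol?** The flow chart lists a urine drug test on the screening night and a combined drug and alcohol test on later nights, so the protocol treats these as different checks. Section 4.2.2 also names the breath test separately from the urine screen.

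**4. How many doses does this concern?** The inputs come from Sections 2.2.1 and 4.7.2. On days 1+2, 16 men receive 20 mg/kg and 16 receive 35 mg/kg, each on one of the two days. For days 3+4, "For the MR-sessions, the same thirty-two subjects will receive 35 mg/kg GHB in one, placebo in the other session".

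- GHB doses: 16 + 16 + 32 = 64, which agrees with two exposures for each of 32 men (Section 11.1).
- At 35 mg/kg: 16 + 32 = 48, and 48/64 = 75%.
- In MR sessions: 32/64 = 50%.

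**5. How many sessions have a specified alcohol test?**

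- PUK-GHB01: 0 of up to 32 × 4 = 128.
- PUK-GHB02: all 20 × 4 = 80 experimental nights.

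The PUK-GHB01 totals are upper limits because Section 4.5.1 says that each man takes part in at least two sessions.

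**6. What happens after a positive alcohol test?** Neither experiment says.

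**The case against.** The strongest reply is that PUK-GHB01 is the lower-dose, waking experiment and includes close contact before dosing. Section 2.2.1 calls its doses low and medium relative to narcolepsy treatment and says they were chosen to limit side effects such as somnolence. Section 3.1.1 places profound sedation around 50 mg/kg, the PUK-GHB02 dose. On days 1+2, blood pressure and pulse are taken at t−40 and t0, CANTAB is run at t−40, questionnaires follow between t−17 and t−10, and blood is drawn at t−30 and t0. The investigator hands over the cup in person. An intoxicated man might well be noticed. Section 2.4 also reports few fatal cases and an acceptable safety profile under controlled use.

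Part of this stands. The contact makes it less likely that obvious intoxication would be missed on days 1+2. However, none of these steps is an alcohol test. On the MR days only a baseline scan is listed before dosing, and every GHB dose there is 35 mg/kg. The protocol nowhere offers the lower dose as a reason for omitting the test, and its alcohol warning carries no dose threshold.

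Two further points are fair. A breath test shows alcohol present at the time and cannot confirm 48 h of abstinence; PUK-GHB02 does not verify the full 48 h either. The gap is therefore a missing check of sobriety before dosing. The documents also show only that no test is specified. The contents of the urine panel are not given, and a site may in practice test for alcohol already. In that case the remedy is to write it down.

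**Conclusion.** The concern holds. PUK-GHB01 manages the alcohol hazard in Section 2.4 by instruction and supervision alone: no alcohol test is specified for any of up to 128 sessions or before any of up to 64 GHB doses. PUK-GHB02 has one before dosing on all 80 experimental nights.

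The conclusion rests on reading the urine screen as a test for drugs only, as both sections that mention it for PUK-GHB01 describe it. It also assumes that Chart 1, whose image is not available but whose caption concerns session order, adds no alcohol test. The number of doses that would actually follow drinking is unknown. Confidence is high in the omission; no estimate of the danger is made. The change should be made because the hazard is serious and named in the protocol, and the remedy is cheap and already in use in the sister experiment.

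**What to change.** - **Section 4.2.1:** add the PUK-GHB02 breath alcohol test before dosing on all four PUK-GHB01 days, together with the urine screen. Test at every session, placebo included, so that the blind is kept.
- **Sections 4.2.1 and 4.2.2:** state that a positive alcohol test postpones the session before the cup is prepared, with a cut-off set by the sponsor.
- **Section 9.1:** replace the alcohol sentence with *Participants must abstain from alcohol for at least 48 h before each session.*
- **Section 12.4:** add one CRF line for the result.

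The cost is at most 128 brief tests with a method already used in PUK-GHB02. The flow chart allows 5 min for the drug and alcohol test together, so the upper bound is 128 × 5 = 640 min, or 640/60 ≈ 10.7 h, over the whole experiment. An occasional session will have to be rescheduled. No extra invasive procedure is needed and no statistical quantity changes.
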